## **B. Evaluation of subclinical atherosclerosis measured by carotid ultrasound at the 6-year follow-up of VIPVIZ, including IMT, carotid plaque prevalence and carotid plaque characteristics.**

*Research questions:*

- What is the development of subclinical atherosclerosis measured by carotid ultrasound within the VIPVIZA treatment arms up to the 6-year follow-up?
- Is there a difference in the degree of subclinical atherosclerosis measured by carotid ultrasound between the treatment arms at the 6-year follow-up?

*Data and variables:* The primary outcomes are carotid IMT and carotid plaque prevalence (categorized as no plaque, unilateral plaque, and bilateral plaque), and carotid plaque area ( $\text{mm}^2$ ).

Secondary outcomes are carotid plaque greyscale median (GSM) and carotid plaque thickness (mm)

*Analyses:*

We will graphically visualize trajectories of mean values and prevalence of outcomes, measured from baseline over 3-year and 6-year of follow-up for the two arms and when stratifying the two arms by baseline age groups.

Development of continuous outcomes (carotid IMT and plaque area) will be analyzed using mixed effects repeated measures with group (II or IC), time point (baseline, 3 or 6 years) and group\*times interaction as fixed factors, assuming an unstructured covariance matrix.

Corresponding analysis of plaque prevalence (one and two-sided, respectively) will be performed using a generalized linear mixed effects model with the fixed effects and a random effect for participant. As group differences at 1 and 3 years are already published(4), only group differences in outcomes at 6 years will be presented. For continuous outcomes, they will be estimated using ANCOVA, adjusted for corresponding baseline value. Group difference of plaque prevalence at 6-years will be evaluated using an ordinal proportional odds model. All ANCOVA/proportional odds models will be fitted with and without adjustments for sex and educational level.

We will also conduct stratified analyses and evaluate intervention effects by

- Sex/Gender (men/women)
- Age-groups at baseline (40, 50 or 60 years).
- Severity of ultrasound result
- Baseline educational level

The main analysis will be performed on complete case data. Analyses using multiple imputation of missing data will be performed as secondary analyses. No correction for multiple comparisons to control the familywise error rate will be performed.

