## **Amendment 2 to the Statistical Analyses Plan**

**Evaluation after 6 years**

**CVD risk scores, CVD risk factors, and ultrasound data**

**2024-01-12**

## **VIPVIZA Amendment 2 to the Statistical Analyses Plan**

The present amendment to the VIPVIZA statistical analysis plan includes details on planned analyses of the VIPVIZA intervention after 6-year follow-up, to be presented in two publications: one evaluating the CVD risk (study A) and one evaluating cIMT and atherosclerotic plaque progression (study B). For the analysis of the 6-year follow-up of VIPVIZA, the description of outcome variables and study populations of the original VIPVIZA statistical plan is still valid, unless otherwise noted in this amendment.

The 3-year follow-up examinations were performed from September 5 2016 to May 28 2019 and all participants from both groups, as well as their respective family physicians in primary care, received the pictorial and written result of the ultrasound examination. Thus, directly after the VIPVIZA 3-year follow-up, all participants in the initial control group (IC) underwent the intervention for the first time and the initial intervention group (II) underwent a second (repeated) intervention. This means that the arms of the trials are no longer parallel and that studies following the progression of the groups after the 3-year follow-up will be post-trial evaluations that no longer allow for estimation of the VIPVIZA intervention effect through direct comparisons of IC and II. Even so, it is still of interest to evaluate the long-term development of the two arms, and to investigate if there still exist group differences in CVD risk and severity of atherosclerosis, e.g. due to the different lag times from when the intervention was given. Furthermore, there are few studies about the development over time of riskfactors and atherosclerosis (assessed by imaging, ultrasonography). Therefore, we will investigate development (regression-progression) of risk factors for CVD and atherosclerosis as assessed by carotid ultrasonography in the complete study population and subdivided in combinations of subgroups, and in particular on age groups (40-, 50- and 60 year old), sex, educational level, severity of ultrasound result. We will also separately analyze scenarios with worst vs best development (e.g. groups of individuals with severe progression vs groups with regression).

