Prevalence ratio of smoking will be estimated from Poisson regression with robust Huber-White sandwich estimator of standard errors, adjusting for baseline smoking status. All ANCOVA/Poisson models will be fitted with and without adjustments for sex and educational level.

For SCORE2, group differences at 1-years and 3 years will be estimated using previously described ANCOVA model.

In addition, we will conduct stratified analyses by:

- Sex/Gender (men/women)
- Age-groups at baseline (40, 50 or 60 years).
- Baseline educational level
- Risk level at baseline
- Severity of ultrasound result

The main analysis will be performed on complete case data. Analyses using multiple imputation of missing data will be performed as secondary analyses. No correction for multiple comparisons to control the familywise error rate will be performed. This is motivated

by the fact that this is a post evaluation of the original trial and does not fall under the convention of adjusting for multiplicity within randomized trials.

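### Study B's 6-year proportional-odds model for plaque prevalence, a primary outcome, names no baseline plaque covariate, although the SAP adjusts its continuous 6-year outcomes and smoking for baseline

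*SAP*

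**What the plan says.** SAP Amendment 2, Study B, lists plaque prevalence in three ordered categories among its primary outcomes. The 6-year rule for continuous outcomes is: "For continuous outcomes, they will be estimated using ANCOVA, adjusted for corresponding baseline value". The next sentence turns to plaque: "Group difference of plaque prevalence at 6-years will be evaluated using an ordinal proportional odds model". Covariates are then given for both model types together: "All ANCOVA/proportional odds models will be fitted with and without adjustments for sex and educational level".

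Study A handles its categorical outcome differently: "Prevalence ratio of smoking will be estimated from Poisson regression with robust Huber-White sandwich estimator of standard errors, adjusting for baseline smoking status".

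Study B has two further elements that can use baseline plaque. The development of plaque over time is to be "performed using a generalized linear mixed effects model with the fixed effects and a random effect for participant". For missing data the plan says "The main analysis will be performed on complete case data" and "Analyses using multiple imputation of missing data will be performed as secondary analyses".

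The introduction to the amendment keeps part of the earlier plan in force: "the description of outcome variables and study populations of the original VIPVIZA statistical plan is still valid". Protocol section 11.5 confirms that plaque is recorded on both sides, so the covariate exists.

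**The concern.** Plaque prevalence is the only primary outcome in either 6-year study whose arm comparison names no baseline term. A categorical scale is no reason for this, since smoking, a secondary binary outcome, is adjusted for its baseline status. The text is silent and does not expressly exclude the covariate, so it may be a drafting slip.

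Two things are at stake:

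- **Precision.** Plaque status at 6 years should depend on plaque status at baseline. Leaving out a strong prognostic covariate weakens the comparison.
- **Selective attendance.** The intervention arm received its ultrasound result after the baseline scan (Protocol 12.2.1). Controls received none (Protocol 12.3) until the 3-year visit. Attendance at 6 years could therefore depend on baseline plaque differently by arm, and an unadjusted complete-case model has no protection against that. No document shows that this happened.

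Silence also leaves the analyst to choose between two different quantities, a marginal and a conditional odds ratio, on a primary outcome.

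**Working it through.** **Text check.** Baseline terms in the 6-year arm comparisons:

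| Outcome | Model | Baseline term named |
|---|---|---|
| Study A, continuous | ANCOVA | yes |
| Study A, smoking | Poisson, robust SE | yes |
| Study B, continuous | ANCOVA | yes |
| Study B, plaque prevalence | proportional odds | no |

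The carry-over clause covers outcome descriptions and study populations, not model covariates. The mixed model addresses development over time, and multiple imputation is secondary. Neither puts baseline plaque into the 6-year comparison.

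**Inputs for the size.** The plan has no figure to reproduce: there is no plaque prevalence, correlation, effect, 6-year attendance or power target for plaque. The only documented input is 3532 participants (protocol amendment, section A), or 3532 / 2 = 1766 per arm. Everything else is assumed:

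- Attendance of 57%: 0.57 × 1766 = 1007, taken as 1000 per arm.
- None/unilateral/bilateral at baseline, then at 6 years in controls: low 75/18/7 then 65/22/13%; middle 60/25/15 then 48/28/24%; high 50/28/22 then 38/30/32%.
- A bivariate normal latent variable for baseline and 6-year plaque, with a shift of 0.12 SD in one arm (marginal odds ratio about 0.82).

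**Method.** Proportional-odds maximum likelihood on expected counts, with arm only or with arm plus two indicators for baseline category. Then z = ln(OR) / SE, power = Φ(|z| − 1.96), and effective sample size ratio = (z adjusted / z unadjusted)².

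**Power, middle scenario, 1000 per arm.** Unadjusted: ln(0.822) / 0.0846 = −2.32, so power is Φ(0.36) = 0.64. Adjusted at correlation 0.7: ln(0.772) / 0.0922 = −2.81, so power is Φ(0.85) = 0.80.

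| Correlation | Adjusted OR | SE | Power | Effective sample size ratio |
|---|---|---|---|---|
| 0.3 | 0.816 | 0.0856 | 0.66 | 1.05 |
| 0.5 | 0.802 | 0.0878 | 0.71 | 1.17 |
| 0.7 | 0.772 | 0.0922 | 0.80 | 1.46 |
| 0.85 | 0.718 | 0.0997 | 0.91 | 2.05 |

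The SE rises with adjustment, but the log odds ratio rises by more. Power is 0.58 without and 0.59 to 0.85 with baseline plaque in the low scenario, and 0.66 without and 0.68 to 0.93 with it in the high scenario. A Monte Carlo check of the middle scenario (4000 trials) gave 0.64 against 0.66, 0.80 and 0.92 at correlations 0.3, 0.7 and 0.85. Adjusted type I error was 0.049 to 0.055.

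A separate simulation used a different model: 1275 per arm, baseline 55/28/17%, conditional odds ratio 0.80, 400 replicates. As baseline plaque became more predictive, power without and with it was 76% and 86%, 60% and 80%, and 41% and 71%.

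**Selective attendance, middle scenario.** There is no arm effect given baseline. Attendance is 57% of 1766 per arm, but lower among baseline plaque carriers in one arm. Ranges run over correlations 0.3 to 0.85.

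| Attendance deficit | Unadjusted OR | Type I error |
|---|---|---|
| 3 points | 0.99 to 0.97 | 0.05 to 0.07 |
| 5 points | 0.98 to 0.94 | 0.055 to 0.10 |
| 10 points | 0.96 to 0.89 | 0.07 to 0.29 |

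The adjusted odds ratio is 1.00 throughout, because attendance was made to depend only on arm and baseline plaque.

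**The case against.** The unadjusted model is valid for the question Study B asks, which is whether the arms differ at 6 years. Chance imbalance in baseline plaque is already inside its standard error, and adjustment changes the estimand. That stands: this is a matter of precision and clarity, not an invalid analysis.

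The size rests on unsourced inputs. The 57% attendance is assumed. The protocol's own planning figure (section 13.1: 3500 with 15% drop-out, so 3500 × 0.85 / 2 = 1487.5 per arm) predates the 6-year extension. At 1500 per arm, unadjusted power is already 0.75, 0.81 and 0.83 in the low, middle and high scenarios, and the gain is about 2 points at correlation 0.3 and about 6 at 0.5. The large gains need correlations of 0.7 or more, which the documents neither support nor exclude.

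The attendance argument is hypothetical, and the remedy is partial. Both arms received their 3-year results, so 6-year attendance may depend on the 3-year scan, and baseline adjustment would not fully remove that.

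The plan also stratifies by severity of the ultrasound finding. If that means the baseline scan, which is not stated, the comparison is shown within levels of baseline disease. This helps, but it does not replace a covariate in the overall comparison.

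The SAP says these post-trial evaluations no longer estimate the intervention effect by direct comparison, and Study B speaks of presenting differences where Study A speaks of testing them. That lowers the stakes. Lastly, only Amendment 2 was supplied. An earlier model rule cannot be ruled out, but the carry-over clause would not bring it in.

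**Conclusion.** The concern holds, with modest weight; it is a point to consider. The gap in the text is clear. Its cost cannot be sized from the documents. Under the assumed scenarios with 1000 per arm, the power gained ranges from about 2 points at correlation 0.3 to 27 points at 0.85. The type I error of the unadjusted comparison stays near 0.05 unless attendance is clearly selective by arm and baseline plaque. These figures show what kind of loss is possible and are not evidence about this trial.

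**What to change.** State in Study B that baseline plaque category (none, unilateral, bilateral) is a covariate in the 6-year proportional-odds model, both with and without sex and educational level. State that the resulting odds ratio is conditional on baseline plaque, and report the unadjusted odds ratio beside it.

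The cost is one or two sentences and a variable already collected. The downside is that the conditional odds ratio lies further from 1 and is not directly comparable with the marginal one: in the middle scenario 0.82 becomes 0.80, 0.77 and 0.72 at correlations 0.5, 0.7 and 0.85. Reporting both deals with this.
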